11.1 Data collection

Designated investigator staff will enter the data required by the protocol into the RAVEX system. Designated investigator site staff will not be given access to the system until they have been trained. Automatic validation procedures within the system check for data discrepancies during and after data entry and, by generating appropriate error messages, allow the data to be confirmed or corrected online by the designated investigator site staff. The Investigator must certify that the data entered into the electronic Case Report Forms are complete and accurate. After database lock, the investigator will receive copies of the patient data for archiving at the investigational site.

The investigator/designee is responsible for assuring that the data (recorded on CRFs) (entered into eCRF) is complete, accurate, and that entry and updates are performed in a timely manner. The Investigator must certify that the data entered are complete and accurate. After final database lock, the investigator will receive copies of the patient data for archiving at the investigational site. All data should be recorded, handled, and stored in a way that allows its accurate reporting, interpretation, and verification.

11.2 Database management and quality control

Novartis staff (or a designated Contract Research Organization (CRO) will review the data entered into the CRFs by investigational staff for completeness and accuracy and instruct the site personnel to make any required corrections or additions. Queries are sent to the investigational site using an electronic data query. Designated investigator site staff is required to respond to the query and confirm or correct the data.

Concomitant medications entered into the database will be coded using the WHO Drug Reference List, which employs the Anatomical Therapeutic Chemical classification system.

Concomitant procedures, non-drug therapies and adverse events will be coded using the Medical dictionary for regulatory activities (MedDRA) terminology.

Laboratory samples will be processed centrally and the results will be sent electronically to Novartis.

ECG readings will be processed centrally and the results will be sent electronically to Novartis.

Data about all study drug(s) dispensed to the patient and all dosage changes will be tracked using an Interactive Response Technology (IRT). The system will be supplied by a vendor, who will also manage the database. The database will be sent electronically to Novartis.

The occurrence of relevant protocol deviations will be determined. After these actions have been completed and the database has been declared to be complete and accurate, it will be locked and the treatment codes will be unblinded and made available for data analysis. Any changes to the database after that time can only be made after written agreement by Novartis Development management.

11.3 Site monitoring

Before study initiation, at a site initiation visit or at an investigator's meeting, a Novartis representative will review the protocol and data capture requirements (i.e. eSource DDE or eCRFs) with the investigators and their staff. During the study, Novartis employs several methods of ensuring protocol and GCP compliance and the quality/integrity of the sites' data. The field monitor will visit the site to check the completeness of patient records, the accuracy of data capture / data entry, the adherence to the protocol and to Good Clinical Practice, the progress of enrollment, and to ensure that study treatment is being stored, dispensed, and accounted for according to specifications. Key study personnel must be available to assist the field monitor during these visits. Continuous remote monitoring of each site's data may be performed by a centralized Novartis CRA organization. Additionally, a central analytics organization may analyze data & identify risks & trends for site operational parameters, and provide reports to Novartis clinical teams to assist with trial oversight.

The investigator must maintain source documents for each patient in the study, consisting of case and visit notes (hospital or clinic medical records) containing demographic and medical information, laboratory data, electrocardiograms, and the results of any other tests or assessments. All information on CRFs must be traceable to these source documents in the patient's file. The investigator must also keep the original informed consent form signed by the patient (a signed copy is given to the patient).

The investigator must give the monitor access to all relevant source documents to confirm their consistency with the data capture and/or data entry. Novartis monitoring standards require full verification for the presence of informed consent, adherence to the inclusion/exclusion criteria, documentation of SAEs, and of data that will be used for all primary variables. Additional checks of the consistency of the source data with the CRFs are performed according to the study-specific monitoring plan. No information in source documents about the identity of the patients will be disclosed.

12 Data analysis and statistical methods

12.1 Analysis sets

For all analysis sets, patients will be analyzed according to the study treatment(s) received.

The Safety Set includes all patients who received at least one dose of study treatment. Patients will be analyzed according to the study treatment received, where treatment received is defined as the assigned treatment if the patient took at least one dose of that treatment or the first treatment received if the assigned treatment was never received.

The PK analysis set will include all patients with at least one available valid (i.e., not flagged for exclusion) PK concentration measurement, who received any study drug and with no protocol deviations that impact PK data.

12.2 Participant demographics and other baseline characteristics

Demographic and other baseline data be listed by patient. Descriptive statistics will be presented for all patients for the Safety set.

Categorical data will be presented as frequencies and percentages. For continuous data, mean, standard deviation, median, minimum, and maximum will be presented.

Relevant medical history, current medical conditions, results of laboratory screens and any other relevant information will be listed by patient.

12.3 Treatments

Concomitant medications and significant non-drug therapies prior to and after the start of the study treatment will be listed by patient.

12.4 Analysis of the primary endpoint(s)/estimand(s)

The primary objective of this study to compare the systemic exposure of mometasone furoate resulting from single orally inhaled doses of QMF149 75/40 administered via the Concept 1 versus the MF Twisthaler[®] (100 μ g) in pediatric asthma patients (≥ 6 to < 12 years of age). All patients evaluated for pharmacokinetic (PK) parameter data will be included in the pharmacokinetic data analysis.

12.4.1 Definition of primary endpoint(s)

The primary PK parameters of interest are Cmax, and AUC0-6h of MF after single dose administration of QMF149 75/40 μ g C 1 and MF TH 100 μ g.

12.4.2 Statistical model, hypothesis, and method of analysis

Log-transformed PK paramters Cmax and AUC(0-6h) will be analyzed for mometasone furoate by linear fixed effects model with treatment and patient as fixed effect. The estimated mean and 90% confidence interval of treatment difference of test vs reference (QMF149 vs MF) will be back transformed to obtain the geometric mean and 90% confidence intervals of the ratio.

12.4.3 Handling of missing values not related to intercurrent event

All drug concentrations below the lower limit of quantification (LLOQ) will be reported as "zero" and will be treated as zero for the calculation of PK parameters.

Patients with missing PK parameters (e.g. Cmax, AUClast, AUCinf) in one period will be excluded from the primary analysis.

In case a certain PK time point is not collected and missing in data, PK parameters may not be calculated from this treatment.

12.5 Analysis of secondary endpoints/estimands

For all safety analyses, the safety set will be used.

12.5.1 Safety endpoints

Adverse events

All information obtained on adverse events will be displayed by treatment sequence and patient.

All treatment emergent AEs will be summarized and listed.

AEs starting on or after the time of the first inhalation of study drug and until 30 days after the last inhalation will be classified as a treatment emergent AE. Any AEs that started during the study after signing informed consent and before the time of the first inhalation of study drug will be classified as a prior AE and will not be included in tabulations of the treatment emergent AEs.

The following treatment emergent AE summaries will be produced:

- by treatment, system organ class and preferred term,
- by treatment, system organ class, preferred term and maximum severity

suspected drug-related AEs by system organ class and preferred term, SAEs by system organ class and preferred term, and AEs leading to discontinuation of study-drug by system organ class and preferred term.

The number and percentage of patients with the most frequent AEs will be summarized by treatment.

Vital signs

All vital signs data will be listed by treatment sequence, patient, and visit/time and if ranges are available, abnormalities (and relevant orthostatic changes) will be flagged. Summary statistics will be provided by treatment and visit/time.

12-lead ECG

PR, QRS, QT, QTcF, and RR intervals will be obtained from 12-lead ECGs for each participant during the study. ECG data will be read and interpreted centrally. All ECG data will be listed by treatment sequence, patientand visit/time, abnormalities will be flagged. Summary statistics will be provided by treatment and visit/time.

Clinical laboratory evaluations

All laboratory data will be listed by treatment sequence, patient, and visit/time and if normal ranges are available abnormalities will be flagged. Summary statistics will be provided by treatment and visit/time.

12.5.2 Pharmacokinetics

Indacaterol and mometasone furoate plasma concentration data will be listed by treatment, patient, and visit/sampling time point. Descriptive summary statistics will be provided by treatment and visit/sampling time point, including the frequency (n, %) of concentrations below the LLOQ and reported as zero.

Summary statistics will include mean (arithmetic and geometric), SD, CV (arithmetic and geometric), median, minimum, and maximum.

Indacaterol and mometasone furoate pharmacokinetic parameters will be listed by treatment and patient. Descriptive summary statistics will include mean (arithmetic and geometric), SD, and CV (arithmetic and geometric), median, minimum, and maximum. An exception to this is Tmax where median, minimum, and maximum will be presented. PK parameters AUC0-6h and Cmax will be used for comparsion of MF exposure after the two treatments. Additional parameters such as Tmax and half-life may be calculated for additional qualitative assessments.

	Non-compartmental pharmacokinetic parameters
AUC0-6h	The AUC from time zero to the last sampling time point 6h (mass x time x volume-1)
AUCinf	The AUC from time zero to infinity (mass x time x volume-1)
Cmax	The maximum (peak) observed plasma, blood, serum, or other body fluid drug concentration after single dose administration (mass x volume-1)
Tmax	The time to reach maximum (peak) plasma, blood, serum, or other body fluid drug concentration after single dose administration (time)
Lambda_z	Smallest (slowest) disposition (hybrid) rate constant (time-1) may also be used for terminal elimination rate constant (time-1)
T1/2	The elimination half-life associated with the terminal slope (λz) of a semi logarithmic concentration-time curve (time). Use qualifier for other half-lives
CL/F	The total body clearance of drug from the plasma (volume x time-1)

 Table 12-1
 Non-compartmental pharmacokinetic parameters

Vz/F	The apparent volume of distribution during terminal phase (associated with λz) (volume)
------	---

12.6 Analysis of exploratory endpoints

Not applicable.

12.7 Interim analyses

An interim analysis is planned to be performed when 12 patients complete both study treatment and there are at least 3 completers in each of the two age groups ≥ 6 to < 9 year olds and ≥ 9 to <12 year olds. The interim analysis will be based on preliminary PK and safety data. An estimate of the systemic exposure as measured by the PK parameter ratios (QMF149 Concept 1 Breezhaler[®] vs MF Twisthaler[®]) together with corresponding 90% confidence intervals will be calculated in order to enable early decision making (e.g., study termination due to having achieved the primary objectives). Rationale for study continuation may include measures such as a review of training procedure for inhaler use by patients or sample size re-estimation.

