Study design	This is an open-label, two-period, single-sequence crossover study including 2 single dose treatments of MF TH 100 μ g and QMF149 75/40 μ g with a washout of at least 4 days between the two treatments. The study will enroll approximately 32 patients with the aim of having 24 completers.	
	The study will include the following:	
	A screening period of up to 14 days	
	Two single-dose treatments separated by a 4-7 day washout period (4 days is the minimum washout)	
	A 30-day investigational drug-free follow-up period	
Study population	Approximately 32 male or female children ≥ 6 years and <12 years diagnosed with asthma will be screened, 24 study completers are required for analysis unless interim analysis determines otherwise.	
Inclusion criteria	 Male and female children ≥ 6 years and < 12 years at the time of study entry. 	
	 Written informed consent by parent(s)/legal guardian(s) for the pediatric patient and assent by the pediatric patient (depending on local 	

		requirements) must be obtained before any study-specific assessment is performed.
	3.	Confirmed documented diagnosis of asthma, as defined by national or international asthma guidelines for at least 6 months prior to study enrollment.
	4.	Patients using low dose ICS as asthma controller therapy for at least 4 weeks prior to first treatment.
	5.	Patients who are familiar with the use of an inhaler device.
	6.	Patients must be able to comply with the Study Visit Assessment Schedule which includes approximately 7 hours on two occasions, and agree to blood draws as scheduled.
	7.	Parents/ legal guardian must be willing and able to attend study visits and assist the child with the procedures outlined in the protocol.
Exclusion criteria	1.	Use of other investigational drugs within 5 half-lives of enrollment, or [within 30 days (for small molecules) /until the expected pharmacodynamic effect has returned to baseline (for biologics)], whichever is longer.
		Patients with weight < 17kg at screening.
	3.	Patients currently taking MF products for any reason at least 7 days prior to Day 1. Patients can enroll if MF was discontinued at least 7 days prior to Day 1 and MF is substituted with a different steroid during entire study duration to avoid its potential impact on PK assessment. These MF products include inhalation, topical and/or nasal spray formulations.
	4.	Patients on medium- and high- dose ICS or any dose ICS/LABA combination.

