Fraction of an aerosol containing particles $< 5 \,\mu$ m in diameter is termed the fine particle fraction (FPF), and is widely used to describe the potential of an aerosol for delivery to the lower respiratory tract (Dolovich 2000). The fine particle mass (FPM), is the mass portion of the nominal dose (i.e. nominal dose \times FPF), which is considered to be delivered to the lungs. MF dose for QMF149 75/40 µg is matched in terms of its FPM (in vitro lung dose) at the corresponding 100 µg MF TH. Systemic availability of MF following oral inhalation is solely due to absorption from lungs since oral bioavailability of MF is low. The FPM of mometasone furoate in QMF149 75/40 µg is matched with MF TH 100 µg. Comparisons of QMF149 75/40 µg delivered via C1 versus MF TH 100 µg in the proposed PK study would compare lung dose

of MF between both formulations and build confidence in dose selection of MF in QMF149 $75/40 \ \mu g$ based on data in patient population. Results from the study will provide opportunity to re-evaluate doses/formulation if needed before proceeding to a larger Phase III study in children.

¹ A single dose of the Asmanex Twisthaler[®] contains 110 μ g of mometasone furoate delivering 100 μ g of mometasone furoate from the inhaler mouthpiece following actuation.

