4.4 Purpose and timing of interim analyses/design adaptations

A planned interim analysis (IA) will be conducted to support decision making when 12 patients have completed both treatment visits (MF TH 100 μ g and QMF149 75/40 μ g) with all planned PK and safety data collected. There must be at least 3 patients within each age strata ≥ 6 to < 9 years and ≥ 9 to < 12 years for the IA to occur. At interim analysis, PK data and safety data will be assessed and a decision will be made to either stop the study or proceed forward to full recruitment. This decision will depend on the ability to confirm the MF dose, or if more data is needed (possibly due to study performance, e.g., the need for better patient training).

For detailed information, refer to Section 12.7

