12.8 Sample size calculation

12.8.1 Primary endpoint(s)

Approximately 32 patients will be recruited in order to obtain 24 completers in this study considering 25% of drop out rate. The sample size of 24 complete patients is considered to yield satisfactory precision in the estimation of the systematic exposure, as measured by the ratio of the PK parameter Cmax, AUC(0-6h) of QMF149 Concept 1 Breezhaler[®] vs MF Twisthaler[®].

With 24 complete patients, the 90% confidence intervals of the PK parameter (AUC (0-6h) and Cmax) ratios (QMF149 Concept 1 Breezhaler[®] vs MF Twisthaler[®]) are expected to be within 72% to 138% with 90% coverage probability. The calculation was based on an assumed 2-fold increase in variability in pediatric population compared to adults who showed intra-patient CV of 30% in the CQMF149E2101 study.

13 Ethical considerations and administrative procedures

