## 2.14 Interim analysis

An iterim analysis is planned to be performed when 12 patients complete both study tractment and there are at least 3 completers in each of the two age groups  $\geq 6$  to 9 < year olds and  $\geq 9$  to  $\leq 12$  year olds. The interim analysis will be based on preliminary PK and safety data. An estimate of the systemic exposure as measured by the PK parameter ratios (QMF149 Concept 1 Breezhaler® vs MF Twisthaler®) together with corresponding 90% confidence intervals will be calculated in order to enable early decision making (e.g., study termination due to having achieved the primary objectives). Rationale for study continuation may include measures such as a review of training procedure for inhaler use by patients or sample size re-estimation.

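### Does the interim analysis need a written criterion for stopping at 12 completers because the objectives are achieved?

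*Protocol*

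**What the plan says.** Protocol 12.7 sets the interim look at 12 patients who have completed both treatments, with at least 3 in each age group. PK ratios with 90% confidence intervals are calculated to support "early decision making (e.g., study termination due to having achieved the primary objectives". SAP 2.14 repeats this almost word for word: "in order to enable early decision making (e.g., study termination due to having achieved the primary objectives". Both then describe the other branch: "Rationale for study continuation may include measures such as a review of training procedure for inhaler use by patients or sample size re-estimation".

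Protocol 4.4 gives the basis for the decision in words: "This decision will depend on the ability to confirm the MF dose, or if more data is needed". The Study population entry of the protocol summary says "24 study completers are required for analysis unless interim analysis determines otherwise".

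The only numerical precision statement is in Protocol 12.8.1, repeated in SAP 3. It concerns the full sample: "With 24 complete patients, the 90% confidence intervals of the PK parameter" ratios are "expected to be within 72% to 138% with 90% coverage probability". It assumes twice the adult within-patient CV of 30%, that is 60%. No equivalence limits, hypothesis or significance level appear in either document. The primary objective is to compare exposure.

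**The concern.** If the objective is only to compare, any estimate could be said to achieve it. Read literally, the study could therefore end at half its planned size on any result. At the planned CV, 12 completers usually give a wider interval than the one used to justify 24.

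Two things would be at stake. The first is precision: the study is meant to support the MF dose before Phase III, and a wide interval supports it weakly. The second is bias: if stopping depended on where the observed ratio fell, the estimate could be pulled in a direction set by the unwritten rule. Treatment is open to the trial team, so a rule fixed in advance would be the usual protection.

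**Working it through.** **Inputs.** From Protocol 12.8.1: 24 completers, adult CV 30%, doubled to 60%. From Protocol 12.7: 12 completers at the interim. From Protocol 12.4.2: 90% intervals from a model with treatment and patient as fixed effects. With two periods this is a paired analysis with n − 1 degrees of freedom.

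**Formulas.** Within-patient SD on the log scale: σ = √ln(1 + CV²) = √ln(1.36) = 0.5545.

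Typical half-width of the log interval: h = t(0.95, n−1) × σ × √(2/n).

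Half-width not exceeded with 90% probability: h × √[χ²(0.90, n−1)/(n−1)].

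**The plan's figure, n = 24.** h = 1.714 × 0.5545 × √(2/24) = 0.2744. Multiplying by √(32.01/23) = 1.180 gives 0.3236, so the interval around a ratio of 1 is 72.4% to 138.2%. This reproduces the stated 72% to 138%.

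**The interim, n = 12.** h = 1.796 × 0.5545 × √(2/12) = 0.4065. Multiplying by √(17.28/11) = 1.253 gives 0.5095, so the interval is 60.1% to 166.4%.

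**Chance that one parameter reaches the 24-completer width.** With limit L this is P[χ²(n−1) ≤ (n−1)(L/h)²]. The stated interval is rounded, so L can be ln(1.38) = 0.322 or −ln(0.72) = 0.329.

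| True CV | n = 12 | n = 24 |
|---|---|---|
| 60% | 19% to 22% | 89% to 92% |
| 50% | 43% to 46% | over 99% |
| 45% | 60% to 64% | about 100% |
| 40% | 78% to 81% | about 100% |
| 30% | 99% | about 100% |

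At n = 12 a 90% chance needs a true CV of about 36% to 37%. If children vary no more than the adults did, 12 completers are enough on this measure. If the planning assumption is right, they usually are not.

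**Is 72% to 138% a success criterion?** Suppose the whole interval had to fall inside that range when the true ratio is 1. This would happen in about 27% of trials at n = 24 and 3% at n = 12, at CV 60%. A criterion that the full sample fails about three times in four cannot be what was meant. The range describes expected width.

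**What a written width rule would do.** Take this rule: stop at 12 if the 90% intervals for both AUC0-6h and Cmax have log half-width at most ln(1.38), otherwise continue to 24. The limit on the SD of within-patient log differences is 0.322 × √12 / 1.796 = 0.621. Dividing by √2 gives σ = 0.439, an observed CV of about 46%. Simulation (200,000 trials per setting, assumed correlation between parameters 0.5 to 0.9) gave:

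| True CV | Trials stopped | 90% interval coverage, stopped trials | Coverage, all trials |
|---|---|---|---|
| 30% | about 98% | about 90% | about 90% |
| 45% | 40% to 50% | about 85% | about 89% |
| 60% | 5% to 12% | 76% to 77% | 89% to 90% |

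The ratio itself stays unbiased, within 0.1% of the truth over all trials. Coverage falls in stopped trials because the rule selects those whose observed variability is low by chance.

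**The case for a change.** The strongest case for a change is that the missing rule costs only a sentence or two to supply, and that without it nobody can later check whether a stop at half the sample was justified. Achieved objectives are the only stopping reason that Protocol 12.7 names, and the summary lets the interim override 24. Nor is the bias always trivial. Under an assumed rule that stops when one parameter's whole 90% interval lies within 72% to 138%, with true ratio 1.25 and CV 30%, about 19% of trials stop. Their average ratio is 1.07, and the average over all trials is 1.23.

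It stands that the criterion is unwritten, that 12 completers are usually less precise at the planned CV, and that a rule tied to the ratio can shift the estimate. Three points limit the weight of this.

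- The bias figures depend on rules that the documents do not contain. At the planned CV the same assumed rule stops about 2% of trials at a true ratio of 1.25 and leaves the overall average at 1.248.
- Protocol 4.4 does give a basis for the decision, if a qualitative one. An imprecise interim result is a plain case of needing more data, and sample size re-estimation is named as one route.
- The width rule is not simply the plan's own standard applied early. It would count a ratio of 2.0 with interval 1.45 to 2.76 (2.0 divided and multiplied by 1.38) as achieved, which does not confirm a dose. It would also stop at an observed CV of 46%, although 90% assurance at 12 completers needs a true CV of about 36%. A rule on the interval's location has the opposite weakness, since it makes stopping depend on the estimate. Statisticians could reasonably disagree about which to prefer.

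**Conclusion.** No change follows. The missing criterion is a gap in detail that the study team can fill sensibly at the interim. There is no type I error to protect, and the result at 12 or 24 completers is a ratio with a 90% interval that shows its own width. A stop at 12 with an interval near 60% to 166% would be visibly weak support for the MF dose, and the background section describes the results as an opportunity to "re-evaluate doses/formulation if needed before proceeding to a larger Phase III study in children". Protocol 9.1.4 in any case lets the sponsor end the study at any time.

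The possible loss is one of precision: 60% to 166% at 12 completers against 72% to 138% at 24, each with 90% probability, if the CV is 60%. It shrinks quickly at lower CVs and has almost gone at 30%. These figures take the point ratio as 1 and apply to each parameter separately; requiring both can only lower the chance of reaching the width. The conclusion rests on the study remaining an estimation study. If an equivalence margin or a formal claim were attached to the ratio, a prespecified stopping rule would be needed.
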